3.4.3 Mixed Model Repeated Measures (MMRM)

The MMRM model will be used to fit change from baseline for continuous endpoints that have data at several post-baseline visits. The model will include all available data from all visits, irrespective of whether the patient discontinued study intervention. Since a repeated measures model is being applied, no imputation will be made for missing data. Region will be added as a random effect. The model will include fixed effects for baseline, visit, study intervention and the baseline by visit and study intervention by visit interactions. An unstructured covariance matrix will be used to describe the correlations on a patient between visits, and the Kenward-Roger correction will be used for degree of freedom approximation in the generation of the model. In the event that the model with unstructured covariance matrix fails to converge, an alternative such as autoregressive or compound symmetry will be used instead. Estimates of the least square (LS) mean change from baseline for each study intervention, and the difference between them (AZD4831-placebo), together with two-sided 90% CI, will be obtained from the model for each visit. The study intervention effect will be tested at the 10% two-sided level of significance.

The reportable results from the model are:

- The LSmeans change from baseline at each visit and their standard errors for each study intervention group.
- The difference in change from baseline at each visit between AZD4831 and placebo (LSmeans difference) together with its two-sided 90% confidence interval (CI).
- The two-sided p-value for the difference in change from baseline at each visit between AZD4831 and placebo.

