3.4.4 Negative binomial regression

Negative binomial regression will be used for the analysis of event rates. In this study the response variable in the model will be either the number of COPDCompEx event or the number of moderate or severe AECOPD exacerbations experienced by a participant. The model will include study intervention group as a fixed effect and logarithm of the participant's corresponding 'at risk' time will be used as an offset variable in the model to adjust for participants having different exposure times during which the events occur. All available data from participants will be included, irrespective of whether they discontinued study intervention.

The model will include study intervention group and geographical region as fixed effects.

The standard parameterization approach (NB2) of the negative binomial model will be applied using PROC GENMOD (SAS procedure).

The estimated annual event rate (AER) for each treatment, the treatment effect (ie, the rate ratio of actual study intervention group versus placebo), corresponding two-sided 90% CI, and two-sided p-value for the rate ratio will be presented. The estimate of the negative binomial overdispersion parameter will also be reported.

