4.2.3.3 Handling of Dropouts

The 'while-on treatment' strategy will be used: which means that if an intercurrent event occurs all subsequent data for that participant are excluded from the evaluation.

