4.2.3.4 Primary Analysis of Secondary Endpoint

Observed values and absolute change from baseline up to Weeks 4, 12 and 24 in post-BD FEV1 will be summarised by each intervention group for the FAS population.

Change from baseline to Week 4, Week 12 and Week 24 in post-BD FEV1 for participants with moderate to severe COPD will be analysed using MMRM as described in Section 3.4.3.

The analysis will be focused on the FAS population.

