4.2.4.4 Primary Analysis of Secondary Endpoint

Observed values and absolute change from baseline up to Weeks 12 and 24 in EXACT total and domain scores will be summarised by each intervention group for the FAS population.

Change from baseline to Weeks 12 and 24 in EXACT (total and domain scores) will be analysed using MMRM as described in Section 3.4.3.

LSMean change from baseline and two-sided 90% CI up to Weeks 12 and 24 in EXACT total and domain scores will be presented in figures. For primary analysis, LSMean change from baseline through Weeks 12 and 24 in EXACT total and domain scores will be presented.

A listing including results from each of the domain and the total EXACT score will be produced for the FAS population.

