4.2.10 Tertiary/Exploratory Endpoint – Annualised rate of COPDCompEx Event

4.2.10.1 Definition

The COPDCompEx definition and derivation are detailed in AZ Business Rules.

Events regardless of what type (i.e., acute worsening or exacerbation) must be separated by at least 14 days in order to count as separate events (i.e., there must be at least 14 days during which no criteria for events are fulfilled).

The time during the event and the 14 days after each event will not be considered when defining time at risk for the COPDCompEx event rate. Time at risk (days) will be defined as

[Date of last dose of study intervention – date of the first dose of study intervention] + 2 – recovery time.

Where recovery time is defined as:

$$\sum_{i=1}^{k} [min(i^{th} event end date + 14, date of last dose of study intervention) - i^{th} event start date + 1]$$

4.2.10.2 **Derivations**

Annualised rate of COPDCompEx events, based on the period from baseline to last dose, will be calculated as:

Annualised rate of COPDCompEx events

Total number of COPDCompEx events

Total number of COPDCompEx events

(Date of last dose of IP – Date of the first dose of IP – recovery time + 2)/365.25

For participants who do not experience an on-treatment COPDCompEx event, date of censoring will be the last dose date or last date of eDiary recording whichever is earlier.

For CompEx analyses, only on-treatment events (i.e., events occurring from randomisation up to and including the last dose day) will be considered.

4.2.10.3 **Handling of Dropouts**

The "while on treatment" strategy, same as defined in section 4.2.1.3.

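### SAP 3.4.3 and 3.4.4 admit data regardless of treatment discontinuation, but the endpoint sections that call them specify while on treatment

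*SAP*

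**What the plan says.** **General model sections**
- SAP 3.4.3 (MMRM): "The model will include all available data from all visits, irrespective of whether the patient discontinued study intervention".
- SAP 3.4.4 (negative binomial): "All available data from participants will be included, irrespective of whether they discontinued study intervention".

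**Endpoint sections that use the MMRM**
- SAP 4.2.3.3 sets while on treatment for post-BD FEV1, "which means that if an intercurrent event occurs all subsequent data for that participant are excluded from the evaluation". The sections for EXACT (4.2.4.3), BCSS (4.2.5.3), Cough VAS (4.2.6.3) and CAT (4.2.7.3) use the same wording.
- Each of the five then calls the general section. FEV1, for example, "will be analysed using MMRM as described in Section 3.4.3".
- SAP 4.2.3.6 repeats the FEV1 analysis under treatment policy, but keeps data after an intercurrent event only up to last dose.
- SAP 4.2.9.3 and 4.2.9.4 run the exploratory spirometry through the same MMRM under treatment policy.

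**Endpoint sections that use the negative binomial model**
- For the COPDCompEx rate, SAP 4.2.10.2 states that "only on-treatment events (i.e., events occurring from randomisation up to and including the last dose day) will be considered". Section 4.2.10.3 sets a while-on-treatment "strategy, same as defined in section 4.2.1.3".
- For the exacerbation rate, SAP 4.2.11.2 covers the period through last dose. Section 4.2.11.3 sets while on treatment by reference to 4.2.2.3.

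**Elsewhere**
- Table 9 assigns while on treatment to the five secondary endpoints (as the primary estimand for FEV1) and to both rates. The output titles in Appendix B carry the same label.
- The opening of SAP 4.2 limits all endpoint analyses to data up to the end-of-treatment (EOT) visit.

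**The concern.** An MMRM that takes every visit whether or not the participant has stopped drug uses the treatment-policy data set. The endpoint sections ask for the while-on-treatment data set and then send the programmer to that MMRM. Two competent programmers could therefore produce different tables under one title, and the choice between them might be made after unblinding.

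At stake is whether off-drug values enter the while-on-treatment estimates for five secondary endpoints. For the two exploratory rates there is a further risk that events and time at risk end on different dates.

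**Working it through.** No figure in the plan rests on this point. The 194 events belong to the primary logrank test, which uses SAP 3.4.1. They reproduce as (1.645 + 0.842)² / (0.25 × (ln 0.70)²) = 194.4 and do not change. The rest is mainly a comparison of text.

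**1. Do both rules govern the same records?** Yes. SAP 4.2.1.3 and the Table 9 footnote list treatment discontinuation as an intercurrent event, with an open category among the reasons. Prohibited medication is the second.

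**2. Rules side by side**

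| Analysis | Rule in the model section it calls | Rule in its own section |
|---|---|---|
| FEV1, main analysis (4.2.3.3, 4.2.3.4) | 3.4.3: all visits | Nothing after the intercurrent event |
| EXACT, BCSS, Cough VAS, CAT (4.2.4 to 4.2.7) | 3.4.3: all visits | Nothing after the intercurrent event |
| COPDCompEx rate (4.2.10) | 3.4.4: all data | Events to last dose day; time at risk to last dose |
| Exacerbation rate (4.2.11) | 3.4.4: all data | Period and time at risk to last dose |
| FEV1, supportive (4.2.3.6) | 3.4.3: all visits | Data after the event kept, but only to last dose |
| Exploratory spirometry (4.2.9) | 3.4.3: all visits | Treatment policy |

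No sentence gives the endpoint section precedence. Only the last row agrees with the general rule.

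**3. Which records are in dispute?** Under Protocol 7.1 and the Schedule of Activities, a participant who stops drug attends the EDV as soon as possible and SV8 about 14 days later. Clinic spirometry, EXACT and CAT are taken at the EDV and not at SV8. The diary, with BCSS and Cough VAS, ends at SV7/EDV. The disputed data are therefore about one visit per discontinuing participant, the diary days between last dose and that visit, and anything recorded after prohibited medication.

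**4. Can such a record become an analysed value?** Yes. SAP Table 1 maps every CAT or EXACT assessment from first dose to Day 127 to Week 12. An off-drug EDV on Day 30, if it is the only post-baseline assessment, becomes the Week 12 value under 3.4.3 and is deleted under 4.2.4.3 and 4.2.7.3. For FEV1 (Table 3), an EDV up to Day 56 falls in the Week 4 window and one on Days 57 to 127 in the Week 12 window.

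**5. Supportive FEV1.** After a discontinuation there is essentially nothing between the intercurrent event and last dose, so a cut at last dose removes the same off-drug data as while on treatment does. Under 3.4.3 read literally, both FEV1 analyses would keep those data. Either way the two analyses do not differ in how they handle discontinuation, which is what the supportive analysis is there to show.

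**6. Illustration for the rates.** Suppose 3.4.4 supplies the events and 4.2.10 or 4.2.11 supplies time at risk to last dose. The assumptions are mine: a fraction d discontinues, the EDV is g weeks after last dose, mean treatment is 18 weeks in the others and 9 weeks in those who stop, and the event rate is constant.
- Relative inflation of an arm's rate = d × g / T, with T = 18(1 − d) + 9d.
- d = 5%, g = 1: 0.05 / 17.55 = 0.3%.
- d = 10%, g = 2: 0.20 / 17.1 = 1.2%.
- d = 20%, g = 4: 0.80 / 16.2 = 4.9%.
- Shift in the rate ratio with unequal discontinuation: 10% against 5% at g = 2 gives 1.0117 / 1.0057 = 1.006; 20% against 5% at g = 4 gives 1.0494 / 1.0114 = 1.038.

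The mismatch is less likely for COPDCompEx, where the event cut-off is written out, than for exacerbations, where the numerator in 4.2.11.2 is simply the total number. For prohibited medication it can run the other way: the cross-referenced rules censor at the intercurrent event, but the time-at-risk formulas run to last dose.

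**The case against.** The strongest reply is that SAP 3.4 only describes methods, and that the data set is fixed repeatedly elsewhere. Each endpoint has its own dropout rule, Table 9 names the strategy, and the output list has separate FEV1 tables for while on treatment and treatment policy. This stands as evidence of intent and shows which sentences to correct. It does not remove two explicit contrary sentences in sections that the endpoints call by number.

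A second reply is that the general sentences may mean only that discontinued participants stay in the model with their eligible data. That would reconcile the texts, but 3.4.3 speaks of all data from all visits.

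Third, 3.4.3 also serves treatment-policy analyses. This is true, and it is a reason for the section to carry no data rule at all.

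Several stronger readings are tempting, and the documents do not support them:
- **All secondary endpoints are affected.** Time to first exacerbation uses 3.4.1, and PK is descriptive.
- **The rate sections exclude everything after an intercurrent event.** They cut at last dose. The intercurrent-event rule reaches them only through references to censoring rules written for time to first event.
- **The visit-window text proves the conflict.** SAP 3.3.3 and 3.3.4 bring EDVs into the windowing. They do not say which estimand retains them.
- **A large dilution follows.** That needs an assumed discontinuation rate, most EDVs falling in one window, and no residual effect soon after stopping a drug that Protocol 2 describes as an irreversible inhibitor.

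**Conclusion.** The contradiction is in the current SAP. It covers five secondary endpoints and, less sharply, two exploratory rates. While on treatment is the intended rule, and the general sentences in 3.4.3 and 3.4.4 are out of line with it. This is a stated rule that is wrong for most of the analyses that call it, not merely missing detail.

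The size of the effect on the MMRM endpoints cannot be derived, because the documents give neither a discontinuation rate nor the delay to the EDV. It is probably modest, since little is collected after last dose. For the rates, the assumed inputs above give an inflation of about 0.3% to 4.9% in one arm and a rate-ratio shift of about 0.6% to 3.8%. These are illustrations, not estimates.

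A reader might infer that the trial's primary estimand is at risk. It is not: the primary logrank and Cox analyses use neither section, and the sample size does not change.

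**What to change.** - Delete the sentences in SAP 3.4.3 and 3.4.4 that admit data regardless of discontinuation. State instead that the data set follows the estimand in each endpoint section: while on treatment for the five secondary endpoints and both rates, and treatment policy for supportive FEV1 and exploratory spirometry.
- In SAP 4.2.10 and 4.2.11, end the counting of events and the time at risk on the same date, including after prohibited medication.
- In SAP 4.2.3.6, replace the cut at last dose with all data collected up to the EOT visit or EDV irrespective of discontinuation, in line with the opening of SAP 4.2.

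The cost is SAP wording and matching changes to the analysis programs, made before unblinding. No new data are needed. The change to 4.2.3.6 does alter the supportive FEV1 data set, so it should be recorded in the SAP amendment history as a change of analysis.

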3.4.4 Negative binomial regression

Negative binomial regression will be used for the analysis of event rates. In this study the response variable in the model will be either the number of COPDCompEx event or the number of moderate or severe AECOPD exacerbations experienced by a participant. The model will include study intervention group as a fixed effect and logarithm of the participant's corresponding 'at risk' time will be used as an offset variable in the model to adjust for participants having different exposure times during which the events occur. All available data from participants will be included, irrespective of whether they discontinued study intervention.

The model will include study intervention group and geographical region as fixed effects.

The standard parameterization approach (NB2) of the negative binomial model will be applied using PROC GENMOD (SAS procedure).

The estimated annual event rate (AER) for each treatment, the treatment effect (ie, the rate ratio of actual study intervention group versus placebo), corresponding two-sided 90% CI, and two-sided p-value for the rate ratio will be presented. The estimate of the negative binomial overdispersion parameter will also be reported.

4 STATISTICAL ANALYSIS

This section provides information on definitions, derivation and analysis/data presentation per domain.

4.1 Study Population

The domain study population covers patient disposition, analysis sets, protocol deviations, demographics, baseline characteristics, medical history, prior and concomitant medication and study drug compliance.

4.1.1 Patient Disposition and Completion Status

4.1.1.1 Definitions and Derivations

Participants screened are those who were enrolled, i.e., participants who agreed/whose legally acceptable representatives agreed to participate in a clinical study following completion of the informed consent process.

Screening failures/participants not randomised are those potential participants who are screened for the purpose of determining eligibility for the study but are not randomly assigned in the study. The investigator will maintain a screening log to record details of all participants screened and to confirm eligibility or record reasons for screening failure, as applicable.

Participants randomized are defined in Section 3.2.

Participants started treatment are all randomised participants who reported at least one administration of the study drug.

Participants completed treatment are participants who completed at least 12 weeks of treatment. Participants who are receiving study intervention between Weeks 12 and 24 at the time the last patient completes Week 12 should attend Study Visit (SV)7 as soon as possible, continuing treatment until they do. They should then attend SV8 14 ± 3 days later.

Participants discontinued treatment are participants who did not complete 12 weeks of treatment due to a permanent discontinuation of the study drug administration.

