1.2 Schema

Figure 1 Study Design

- ^a SV1 assessments may occur at any time during screening, including SV2, all must occur within the screening window. Informed consent must be obtained before any study procedure. Informed consent can be taken prior to SV1.
- To reduce the burden on participants, Visits SV2, SV4, SV7/EDV, and SV8 will have a limited number of assessments and shortened duration.
- ^c Visit SV2 should occur 14 to 16 days before SV3 (Day 1).
- Participants discontinuing study intervention before SV7 should attend site for SV7 assessments as soon as possible as an EDV, then attend for SV8 assessments 14 (± 3) days later.

Enrolment will be stopped after at least 194 first COPDCompEx events have occurred. At this point, all participants enrolled in the study that have not yet completed SV5 should continue in the study to complete 12 weeks of treatment. For these participants SV5 and SV7 should be combined into one visit. Participants who have already completed 12 weeks of treatment when study enrolment is stopped should attend SV7 as soon as possible, continuing treatment until they do. All participants should attend SV8 14 ± 3 days after SV7/EDV.

EDV = early discontinuation visit; FU = follow-up; SoC = standard of care; SV = Study Visit.

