- The study will explore an alternative community-based patient recruitment in some countries, utilising a network of Primary Care and Community COPD/Pulmonary Rehabilitation facilities to boost enrolment. The target countries with established Community COPD Clinic/Pulmonary Rehabilitation infrastructure will serve as participant recruitment centres or new sites.

- Enrolment will be stopped after at least 194 first COPDCompEx events have occurred. At this point, all participants enrolled in the study that have not yet completed SV5 should continue in the study to complete 12 weeks of treatment. For these participants SV5 and SV7 should be combined into one visit. Participants who have already completed 12 weeks of treatment when study enrolment is stopped should attend SV7 as soon as possible, continuing treatment until they do. All participants should attend SV8 14 ± 3 days after SV7/EDV.
- The URC will review efficacy data from the IA and the DRC will perform periodic safety monitoring with a focus on skin reactions and pneumonia. See Appendix A 5 for details.
- To reduce the burden on participants, Visits SV2, SV4, SV7, and SV8 will have a limited number of assessments and shortened duration, and Visit SV6 will be a "virtual visit" which will be performed away from the study site. This will be conducted over the same telemedicine video conferencing facility that is being used for the virtual spirometry during other visits in the study and is based on technology provided by Zoom Inc (San Jose, California, USA), through the UNIFY platform, using a provisioned handheld device.
- The entire study period is planned to take between 18 and 30 weeks for each individual participant: a 4-week screening period, minimum 12 weeks to a maximum 24 weeks of dosing and 2 weeks of follow-up.

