7.1.4 Participant Discontinuation at Study End

Enrolment will be stopped after at least 194 first COPDCompEx events have occurred. At this point, all participants enrolled in the study that have not yet completed SV5 should continue in the study to complete 12 weeks of treatment. For these participants SV5 and SV7 should be combined into one visit. Participants who have already completed 12 weeks of treatment when study enrolment is stopped should attend SV7 as soon as possible, continuing treatment until they do. All participants should attend SV8 14 ± 3 days after SV7/EDV.

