3.3 General Considerations

Study design

This is a Phase IIa, randomised, placebo-controlled, double-blind, parallel-arm, event-driven study with an up to 24-week treatment time designed to evaluate the efficacy and safety of AZD4831 administered QD using a tablet in adult patients with confirmed moderate to severe symptomatic COPD (FEV1/FVC < 0.7, ≥ 10 pack-years smoking history, and post-BD FEV1 ≥ 25% predicted) who are at high risk of exacerbations despite being maintained on optimised SoC inhaled therapies - triple inhaled therapy (ICS/LABA/LAMA) or ICS/LABA dual therapy or LABA/LAMA dual therapy (for participants with a history of pneumonia or who are otherwise deemed unsuitable for ICS). The treatment will be over a minimum 12-week and maximum 24-week period. Further details about inclusion and exclusion criteria are available in Section 5 − Study population in the CSP.

Approximately 406 participants will be randomised 1:1 to AZD4831 QD or placebo QD. The randomisation will be stratified by country. The study will be blinded to both participants and investigators/site staff as well as to the sponsor.

The entire study period is planned to take between 18 and 30 weeks for each individual patient: a 4-week screening period, minimum 12 weeks to a maximum 24 weeks of dosing and 2 weeks of follow-up. The enrolment will be stopped after approximately 194 COPDCompEx events have occurred, and when the last enrolled patient completes 12 weeks of treatment, the study will stop. At the point the study ends due to the required number of COPDCompEx events occurring, participants who are receiving study intervention between Weeks 12 and 24 at the time the last patient completes Week 12 should attend SV7 as soon as possible, continuing treatment until they do. They should then attend SV8 14 ± 3 days

later. For further details and the Schedule of Activities, refer to Table 1 – Schedule of Activities in the CSP.

Study product

The study product is AZD4831 and it will be administered orally once a day as tablet containing 5 mg of investigational product (IP). The first dose of study intervention will be administered in clinic on the day of randomisation. Participants will receive study intervention at the site on visit days and at home between visits. No dose modification is allowed during the study.

Sample size determination

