4.1.1.2 Presentation

Patient dispositions (number and percentage) of subjects enrolled, subjects not randomised (incl. reasons), subjects randomised, subjects randomised and who did not receive treatment, subjects who started treatment, subjects who completed the treatment, subjects who discontinued treatment (incl. reasons), subjects included in the cough substudy, subjects who completed the study and subjects withdrawn from study (incl. reasons) will be presented in a summary table for each study intervention group and overall. A listing including all standardised disposition terms will also be provided for all discontinued subjects and subjects completing the study. Both the table and the listings will be based on the screened set.

To demonstrate balance in stratification factor categories (i.e. countries), the number and percentage of participants in each category will be summarised by study intervention group and overall focusing on the randomised set.

The recruitment per country and site will be provided based on the screened set, while the global/country situation study disruption will be summarised on the full analysis set.

The number and percentage of participants with one or more disruption due to COVID-19 pandemic will be presented by study intervention group considering the participants valid for the full analysis set. A listing of all the participants affected by COVID-19 related study disruption will be produced by unique patient number identifier, investigational site, and a description of how the individual's participation was altered. COVID-19 related study disruptions can be:

- Visit related (if visit is impacted by global/country situation, then contact mode will be specified);
- Study drug related (if study drug action taken (except "Drug Withdrawn") was impacted by global/country situation; study drug administration or location was impacted by global/country situation; who performed a study drug administration);

- Discontinuation of study drug due to COVID-19 pandemic (if study drug action taken "Drug Withdrawn" was impacted by global/country situation);
- Withdrawal from study (if primary reason for ending study is related to global/country situation).

Randomisation scheme and codes as well as participants receiving the various batch of investigational product will also be listed for all randomised participants.

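### The disposition table counts premature treatment stops after Week 12 as completions and drops their reasons, although planned dosing runs to Week 24 or to the study-end SV7

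*SAP*

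**What the plan says.** SAP 4.1.1.1 sets two complementary rules. On one side, "Participants completed treatment are participants who completed at least 12 weeks of treatment". On the other, "Participants discontinued treatment are participants who did not complete 12 weeks of treatment due to a permanent discontinuation of the study drug administration". SAP 4.1.1.2 then builds the disposition summary (Table 14.1.1) on them: numbers completing and discontinuing treatment, by arm, with reasons for the discontinuations only.

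Protocol 4.1 plans a "minimum 12 weeks to a maximum 24 weeks of dosing", and SAP 3.3 repeats that range. Protocol 1.2 treats any stop before the Week 24 visit as early: "Participants discontinuing study intervention before SV7 should attend site for SV7 assessments as soon as possible as an EDV". Protocol 7.1 lists the grounds for permanent discontinuation without a 12-week limit.

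Protocol 7.1.4 describes the one planned route to a shorter course. When enrolment stops, participants not yet past SV5 finish at 12 weeks with SV5 and SV7 combined, and those already past 12 weeks attend SV7 as soon as possible.

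**The concern.** The 12-week cut treats two different things alike. A participant whose SV7 is brought forward by the study-end rule has finished as planned. A participant who gives up the drug at Week 16 while enrolment is still open has not. Under SAP 4.1.1.1 both are completers.

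At stake is the table from which readers take the number of treatment discontinuations per arm and why they happened. Because the primary estimand censors at treatment discontinuation, that breakdown is also what a reader uses to judge whether censoring might be informative. As defined, it covers only the first half of the maximum treatment period.

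**Working it through.** **1. The rules applied to four participants**

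| Participant | What happens | SAP 4.1.1.1 | Against the protocol plan |
|---|---|---|---|
| A | Takes drug to Week 24 | Completed | Planned end reached |
| B | At Week 16 when enrolment stops; attends SV7 | Completed | Planned study-end stop |
| C | Week 16, enrolment open; withdraws consent to treatment | Completed, no reason shown | Early discontinuation, EDV required |
| D | Week 8, same reason as C | Discontinued, reason shown | Early discontinuation, EDV required |

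B and C receive the same label although only B followed the plan. C and D took the same decision but receive different labels.

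**2. Where a stop like C's appears elsewhere, by reason**

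- Adverse event: SAP 4.7.2.1 defines AEs leading to discontinuation with no time limit. They appear by arm in Tables 14.3.5.1 and 14.3.5.2, the rash stops also in Table 14.3.2.1, and narratives are written.
- Lack of efficacy: under SAP 4.2.1.1 such a stop is itself a COPDCompEx event, but no table of reasons counts it.
- Withdrawn consent to treatment, non-compliance, other: no table. The row for withdrawal from study need not catch them. Protocol 7.1 keeps such participants in the study, and under protocol 4.4 a participant seen through SV8 can count as completing it.

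**3. Size**

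The documents give no discontinuation rate to reproduce. The plan's event target does not use these categories. It reproduces as 4 × (1.6449 + 0.8416)² / 0.3567² = 194.4, against 194 in protocol 9.2.

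For illustration, let d be the assumed proportion stopping prematurely by Week 24 if scheduled for 24 weeks, with constant hazard h = −ln(1 − d)/24.

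*Everyone scheduled for 24 weeks.* Share relabelled = exp(−12h) − exp(−24h) = √(1 − d) − (1 − d).

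- d = 10%: 0.9487 − 0.9000 = 4.87 points
- d = 25%: 0.8660 − 0.7500 = 11.60 points

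*Study-end rule of protocol 7.1.4 applied.* Assume uniform accrual over A weeks and SV7 at the moment enrolment stops. A fraction 12/A is planned to stop at Week 12, another 12/A between Weeks 12 and 24, and (A − 24)/A at Week 24. The average share is

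((A − 24)/A)·[exp(−12h) − exp(−24h)] + (1/A)·[12·exp(−12h) − (exp(−12h) − exp(−24h))/h].

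The accrual periods are assumptions, as the documents state none. Counts per arm use the 203 of protocol 9.2.

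| Schedule | d = 10%: points (per arm) | d = 25%: points (per arm) | Share of all premature stops |
|---|---|---|---|
| A = 39 weeks | 2.63 (5.3) | 6.29 (12.8) | 34% to 32% |
| A = 52 weeks | 3.19 (6.5) | 7.62 (15.5) | 38% to 36% |
| A = 78 weeks | 3.75 (7.6) | 8.95 (18.2) | 42% to 40% |
| All to Week 24 | 4.87 (9.9) | 11.60 (23.6) | 49% to 46% |

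**The case against.** The threshold has a design reason. Twelve weeks is the minimum planned for everyone, and SAP 4.1.1.1 follows the definition directly with the study-end arrangement. Requiring 24 weeks of all participants would mislabel planned stops as failures. That stands, and it rules out a plain 24-week definition. It does not justify labelling unplanned stops as completions.

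Tolerability is not read from this table alone. Late AE stops are reported by arm and cause in the safety tables, and SAP 4.7.1.2 plots the percentage still exposed over time and tabulates exposure in bands to Day 172. The AE part stands in full: a reader who inferred that late stops for rash or pneumonia are hidden would be wrong. The exposure outputs help less, because they give no reasons and mix planned study-end stops with premature ones.

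The size is uncertain, and some features point downwards. Protocol 4.3 reports rash in healthy subjects around 7 to 10 days after first dose; stops of that kind would fall before Week 12 and be classified correctly. This also stands. A reader might conclude that about half of all discontinuations are relabelled, but that needs everyone scheduled for 24 weeks, contrary to protocol 7.1.4.

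**Conclusion.** The point holds for the disposition table. Followed exactly, the SAP counts premature permanent stops after Week 12 as completions and leaves their reasons out of Table 14.1.1. The loss falls mainly on non-AE reasons and on the overall discontinuation count by arm. The illustrative size is about 2.6 to 11.6 percentage points. It rests on a constant hazard, an assumed 10% to 25% stopping by Week 24, and either uniform accrual over at least 39 weeks or a full 24-week schedule for all. It is smaller if stops cluster early.

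A reader might go further and infer that late stops also escape the intercurrent-event rule, so that off-drug values stay in the while-on-treatment mixed models. The documents do not support this. Treatment discontinuation is an intercurrent event in SAP Table 9 and 4.2.1.3 with no 12-week limit. Primary censoring uses the last dose, last eDiary date or intercurrent-event date (4.2.1.2, 4.2.1.3), and the on-treatment period in 3.3.2 ends no later than the last dose. None of these refers to the disposition categories. The primary test, power and censoring rule are unaffected. This is a correction to reporting that should be made.

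**What to change.** In SAP 4.1.1.1:

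- Define completed treatment as study drug taken to Week 24, or to the SV7 (or combined SV5/SV7) triggered by the study-end rule in protocol 7.1.4.
- Define discontinued treatment as any other permanent stop, at any time, and tabulate it by arm with its reason.
- Keep completion of 12 weeks as an additional row in Table 14.1.1.

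Before the flag is programmed, reconcile the study-end wording. Protocol 7.1.4 ties the early SV7 to the stop of enrolment, whereas SAP 3.3 and 4.1.1.1 tie it to the time the last patient completes Week 12. The two would classify some stops between Weeks 12 and 24 differently.

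The cost is a revised definition and one derived flag. Protocol 6.5 already has intervention stop dates recorded in the eCRF, and the SAP already plans to report reasons for stops before Week 12, so no new data collection appears necessary. The downside is a slightly less favourable reported completion rate.
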